7.4 Supportive Medications

Colony Stimulating Factors

Colony stimulating factors including filgrastim (G-CSF; Neupogen) and peg-filgrastim (peg-GCSF; Neulasta) may be employed for primary and secondary prophylaxis according to American Society of Clinical Oncology (ASCO) Guidelines.

Corticosteroids

Use of corticosteroids is currently recommended for patients with COVID 19 and hypoxia,⁵⁹ Use of dexamethasone (or equivalent corticosteroid) at doses of 6 mg daily for 10 days is allowed. Further use of corticosteroids for COVID 19 is discouraged but use for management of unrelated chronic medical illnesses (e.g. COPD exacerbation) will be allowed at doses equivalent to ≤ 20 mg prednisone daily.

Anti-Emetics

Prophylactic and other antiemetic therapy will be given at the discretion of the treating physician but should not routinely include corticosteroids.

Antimicrobial Prophylaxis

Prophylaxis for varicella zoster virus (VZV), herpes simplex virus (HSV), or pneumocystis pneumonia (PJP) prophylaxis is allowed, but not required or recommended.

7.5. Perioperative/Periprocedural Management

The following guidance should be applied during the perioperative period for patients who require surgical intervention or an invasive procedure while receiving ibrutinib:

For any planned surgery or invasive procedure requiring sutures or staples for closure, ibrutinib should be held for at least 7 days prior to the intervention and should be held at least 7 days after the procedure, and restarted at the discretion of the investigator when the surgical site is reasonably healed and without serosanguinous drainage or the need for drainage tubes.

For planned minor procedures (such as needle biopsy, thoracentesis, or paracentesis) ibrutinib should be held for at least 3 days prior to the procedure and should not be restarted for at least 3 days after the procedure. It is not necessary to hold ibrutinib for bone marrow biopsies, intubation or central line placements.

For emergency procedures, ibrutinib should be held after the procedure until the surgical site is reasonably healed, for at least 7 days after the urgent surgical procedure or 3 days for an urgent minor procedure, or at the discretion of the investigator.

7.6. Duration of Treatment

Study treatment will continue for a total of 2 cycles (14 days). Therapy will also be discontinued if

- Toxicity requiring unacceptable dose suspension or reduction as outlined in Section 7.1.
- Patient voluntarily withdraws from the study
- The treating physician decides it is no longer in the best interest of the patient to continue study treatment

7.7. Duration of Follow-up

Patients will be followed for up to 12 months or until death or withdrawal of consent from study assessments and all further follow-up. Patients who discontinue therapy should continue to be followed for study assessments according to the study calendar. Following hospitalization, study visits will be telephone or video encounters. Patients will need to return to OSU when feasible for laboratory studies as outlined in the study calendar and in line with institutional criteria for discontinuation of isolation at the outpatient setting.

7.8. Criteria for Removal from Study

Patients will be removed from the study if they die or if they withdraw consent from study assessments and all further follow-up. Discontinuation of therapy alone is not sufficient for removal from study. Date of study removal and reason will be documented in the case report form.

For subjects who withdraw consent, there must be clear documentation of whether the subject withdraws consents to treatment only (i.e. agrees to follow-up) or withdraws consent to treatment and follow-up.

7.9. Duration of Study

The study will end 12 months after the final patient is enrolled.

8. DOSE DELAYS AND MODIFICATION (Only Applicable to Safety lead-in patients who do not have DLT, and Phase 2 Patients)

8.1. Guidelines for Dose Suspension or Modification Due to Adverse Events

Adverse events (AEs) will be assessed and graded according to the National Cancer Institute Common Terminology Criteria for Adverse Events (CTCAE) version 5.0. Laboratory toxicities will be formally evaluated on days 8, 15, 22, and 29, unless determined to be clinically irrelevant by the principal investigator. These labs will be done \pm 3 days.

Treatment with study drug should be interrupted for any grade 3 or higher non-hematologic toxicity with at least possible association to ibrutinib, with the exception of electrolyte abnormalities, nausea, vomiting, or diarrhea, alopecia, or hypertension that can be managed with supportive medications.

Treatment with study drug should be interrupted for any grade 4 hematologic toxicity (or increase in grade by 2 levels if baseline toxicity exists) with at least possible association to ibrutinib with the exception of neutropenia that can be managed with growth factors, anemia/thrombocytopenia responsive to transfusion, or lymphocytosis/lymphocytopenia.

Once the toxicity has resolved to grade 1 or baseline, study drug can be restarted at the original dose. If toxicity recurs, the dose should be held and then decreased by one dose level as outlined in Table 2.

If drug needs to be held > 14 days and still considered possibly drug-related, study drug should not be restarted.

Table 2: Dose De-Escalation Schedule for Toxicity

Dose De-Escalation Schedule for Toxicity	
Dose Level	Study drug
Level 1 – Starting Dose	420 mg/day (Days 1-14)
Level 2	280 mg/day
Level 3	140 mg/day
Level 4	Discontinue

8.2. Dose modification of study drug (Ibrutinib or placebo) for Hepatic Impairment

Patients who develop grade 2 increase in bilirubin or ALT/AST should have study drug dose reduced to 2 capsules (equivalent to 280 mg daily) for either arms. If liver function tests return to grade 1 levels, study drug can be increased to 3 capsules (equivalent to 420 mg daily). Patients who develop grade 3 or higher increase in bilirubin or AST/ALT or who have evidence of hepatic failure should have study drug discontinued permanently.

8.3 Unblinding Procedures

Unblinding can be done only in cases of an emergency leading to a life threatening unexpected adverse event that is at least possibly related to the investigational agent and for which unblinding would influence treatment decisions. As well, unblinding would be considered in a situation where knowledge of the arm would determine whether a procedure

could be performed emergently (because of risk of bleeding). In any case of unblinding, the patient will be discontinued from the protocol drug.

9. ADVERSE EVENT ASSESSMENT AND REPORTING

9.1. Safety Assessment Overview and Monitoring Timeframe

To monitor the toxicity of study treatment and ensure safety of subjects enrolled in this interventional study adverse events (AEs) will be assessed at each study visit and described and graded according to the National Cancer Institute Common Terminology Criteria for Adverse Events (CTCAE) version 5.0. In general, AEs and serious adverse event (SAEs) should be reported as a diagnosis instead of symptoms if possible at the time of reporting.

All AEs and SAEs whether volunteered by the patient, discovered by study personnel during questioning, or detected through physical examination, laboratory test, or other means will be reported appropriately. Each reported AE or SAE will be described by its duration (i.e. start and end dates), regulatory seriousness criteria if applicable, suspected relationship to the study drug, and actions taken.

The study period during which all AEs and SAEs must be reported begins after the patient is randomizes and ends at 30 days post completion of treatment. After this period investigators should only report SAEs that are attributed to prior study treatment.

Maintenance of Safety Information

All safety data should be maintained in a clinical database in a retrievable format. The INSTITUTION and PRINCIPAL INVESTIGATORS shall provide all adverse events, both serious and non-serious, in report format. However, in certain circumstances more frequent provision of safety data may be necessary, e.g. to fulfill a regulatory request, and as such the data shall be made available within a reasonable timeframe.

All adverse events and special situations, whether serious or non-serious, related or not related, following exposure to study drug (ibrutinib or placebo) are to be documented by the investigator and recorded in the CRF and in the subject's source records. Investigators must record in the CRF their opinion concerning the relationship of the adverse event to study drug.

All (serious and non-serious) adverse events reported for study drug should be followed-up in accordance with clinical practice.

9.2. Definition of an Adverse Event (AE)

An AE is any unfavorable and unintended sign, symptom, or disease temporally associated with the use of an investigational medicinal product (IMP) or other protocol-imposed

intervention regardless of attribution. The event does not necessarily have a causal relationship with that treatment or usage.

This includes the following:

- An exacerbation or an unexpected increase in frequency or intensity of a pre-existing condition (other than condition under investigation) including intermittent or episodic conditions.
- Significant or unexpected worsening or exacerbation of the condition/indication under investigation.
- A suspected drug interaction.
- An intercurrent illness.
- Any clinically significant laboratory abnormality.

An AE does not include:

- Anticipated day-to-day fluctuations of any pre-existing conditions including the disease under study.
- Signs and symptoms of the disease under study that do not represent a significant worsening or exacerbation.
- Expected progression of the disease under investigation.

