3.2. Secondary Endpoints

- Time from study initiation to 48 hours fever-free (<100.5 degrees F orally)
- Duration of hospitalization
- Time in ICU
- Time to ICU admission
- Number of days requiring supplemental oxygen (or supplemental oxygen above baseline levels)
- Total days of mechanical ventilation
- Time to mechanical ventilation
- Shock and need for pressure support

- Incidence of any infection (viral, fungal, bacterial) including opportunistic infections
- Time to clinical resolution
- Grade 3 or higher toxicity
- Viral clearance at the end of therapy
- Time to viral clearance
- Overall survival at 3 and 12 months

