9.3. Definition of a Serious Adverse Event (SAE)

An AE that meets one or more of the following criteria/outcomes is classified as serious:

- Death.
- Life threatening.
- Disabling/incapacitating.
- Results in new hospitalization or prolongs a hospital stay.
- A congenital abnormality.
- Other serious medical events may also be considered SAEs if it is an important medical event that may not be immediately life threatening or result in death or hospitalization, but based upon appropriate medical and scientific judgment may jeopardize the patient or may require medical or surgical intervention to prevent one of the other serious outcomes listed in the definition above.

Death for any reason must be reported as a SAE.

A SAE does not include:

- Progression of the underlying infection or syndrome (COVID-19).
- Hospitalization for a routine clinical procedure or treatment as required by the protocol.

- Hospitalization for non-medical reasons (i.e., social admissions, hospitalizations for social, convenience, or respite care).

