Primary Endpoint Analysis: All randomized patients will be included in the primary endpoint analysis and analyzed in the treatment arm to which they were randomized (ITT population). The data will be analyzed using a one-sided Fisher's exact test and a promising signal declared if $p \leq 0.20$ and the event rate is lower in the experimental arm. Since the primary endpoint is to be measured within the first 30 days of registration, we do not expect that primary endpoint information will be missing. However, if there is data missing, the patient will be considered a treatment failure.

Sensitivity analyses include comparison between treatment arm when adjusting for stratification factors and other important variables such as type of cancer or more refined categories of standard of care therapy via logistic regression. If there are events for respiratory failure based on clinical diagnosis without an objective measure and driven solely by resource limitation or if patient has DNI (Do Not Resuscitate) status, a sensitivity analysis will compare arms excluding patients with these events. Sensitivity analyses will be performed for the ITT population and for eligible patients who receive their assigned therapy without a major protocol violation.

Adverse Event Stopping Rules: If there is no concerning safety signal in the lead-in cohort, and the study is able to continue to the randomized component as planned, we have included a plan for comparing toxicity at the interim analyses (first 30 patients across both arms). Accrual will be temporarily suspended to this study and discussion of the data with co-investigators and the data safety monitoring board will occur if we observe adverse events that satisfy the following criteria:

- If the percentage of grade 3/4 all-cause adverse events is at least 15% higher in the ibrutinib arm than in the standard of care arm. This would also include grade 2 hemorrhage if considered significant by the treating physician in collaboration with PI.
- If the percentage of grade 4 all-cause adverse events is at least 15% higher in the ibrutinib arm than in the standard of care arm
- If the percentage of grade 5 treatment-related adverse events is at least 5% higher in the ibrutinib arm than in the standard of care arm

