We note that the above stopping rules may be adjusted at any time during the conduct of the trial and in consideration of newly acquired information regarding the adverse event profile of the treatment(s) under investigation. The study team may choose to suspend

accrual because of unexpected adverse event profiles that have not met the specified rules above.

Secondary Endpoints: At the final analysis, all adverse events will be summarized by grade, type, and attribution (regardless of attribution and treatment-related) for each arm. Time-to-event endpoints such as time to discharge and overall survival will be estimated for each arm using the method of Kaplan-Meier. Medians estimates and/or estimates at specific time points will be provided with 95% confidence intervals. The proportion of patients with viral clearance at the time of hospital discharge will be estimated with 95% confidence intervals for each arm. For all biomarkers, descriptive statistics (e.g., means, medians, standard deviations, interquartile range) and graphical displays will be used to characterize central tendency and variability over time. Values will be log transformed as appropriate to reflect biologic plausibility. We will evaluate for statistical trends over time among the biologic measurements, with multiple measurements per patient, using mixed effects models. Lastly, associations between baseline characteristics and the primary endpoint will be evaluated with logistic regression, adjusting for arm. These analyses will be largely descriptive, as a result of a limited sample size.

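### Section 9.2 both includes and excludes significant but expected COVID-19 progression as an adverse event, so the all-cause grade 3+ comparison between arms depends on which line is followed

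*Combined protocol and SAP*

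**What the plan says.** Section 9.2 lists what an adverse event includes, among it "Significant or unexpected worsening or exacerbation of the condition/indication under investigation". Its list of what is not an adverse event contains "Expected progression of the disease under investigation" and "Signs and symptoms of the disease under study that do not represent a significant worsening or exacerbation".

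Section 9.3 says that progression of COVID-19 is not an SAE, but also: "Death for any reason must be reported as a SAE". Section 9.4 defines expectedness only against the ibrutinib Investigator's Brochure.

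Section 2.2 has a secondary objective on grade 3 or higher toxicity by arm, and Section 3.2 lists "Grade 3 or higher toxicity" as the endpoint. Neither says whether COVID-19 events belong in it. In Section 13, "all adverse events will be summarized by grade, type, and attribution (regardless of attribution and treatment-related) for each arm".

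**The concern.** Respiratory failure from COVID-19 is a significant worsening. It is also progression that the design expects: Section 13 assumes respiratory failure or death in 40% of controls. So the trial's main efficacy event can be recorded as an adverse event under one line of 9.2 and left out under another, and two investigators could treat the same event differently.

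If such events are counted, the all-cause grade 3+ comparison partly repeats the efficacy result. A drug that prevents respiratory failure then looks less toxic in that summary for a reason unrelated to its own toxicity. If they are not counted, the summary reflects other toxicity, except that deaths still enter through 9.3.

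**Working it through.** **Where the lines of 9.2 conflict.** The inclusion line joins its two conditions with an or, which gives three cases:

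- Worsening that is unexpected: counted, and no exclusion applies.
- Symptoms that are not a significant worsening: excluded, consistent with the inclusion line.
- Progression that is significant but expected: counted by one line and excluded by another.

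Only the third case is in conflict. Expected progression of COVID-19 is not defined in 9.2, and 9.4 does not help.

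**Inputs.** COVID-19 event rates are 40% placebo and 15% ibrutinib (Section 13, Design and Sample Size). As a check that these are the rates the design uses: the Casagrande-Pike-Smith correction gives an effective 30 × (1 − 1/(30 × 0.25))² = 22.53 patients per arm. A pooled z-test at one-sided 0.20 with the interim futility stop then returns the stated power of 82.8%. The plan gives no figure for toxicity. The other grade 3+ rates below are therefore assumptions: 20% placebo and 30% ibrutinib, independent of COVID-19 events.

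**Formula.** Let f be the share of COVID-19 events that enter the AE count, the same in both arms. A patient has a grade 3+ event with probability 1 − (1 − f × COVID-19 rate)(1 − other rate).

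- Ibrutinib: 1 − (1 − 0.15f)(0.70) = 0.30 + 0.105f
- Placebo: 1 − (1 − 0.40f)(0.80) = 0.20 + 0.32f
- Difference, ibrutinib minus placebo: 10 − 21.5f percentage points

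**Results.**

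| Reading | f | Ibrutinib | Placebo | Difference |
|---|---|---|---|---|
| No COVID-19 event counted | 0 | 30.0% | 20.0% | +10.0 |
| A quarter counted | 0.25 | 32.6% | 28.0% | +4.6 |
| Half counted | 0.5 | 35.25% | 36.0% | −0.75 |
| All counted | 1 | 40.5% | 52.0% | −11.5 |

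Deaths count under either reading. If a share s of COVID-19 events is fatal, excluding progression gives 10 − 21.5s, not 10. The documents do not give s. The two readings differ in sign only while 10 − 21.5s is above 0, that is, for s below 10/21.5, about 47%. Above that, both readings favour ibrutinib.

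**Sensitivity, all events counted.**

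- Overlap, at 20% v 30%: no patient with both kinds of event, 45% v 60%, −15; complete overlap, 30% v 40%, −10.
- Other rates (placebo v ibrutinib), independent: 10% v 20% gives 32% v 46%, −14; 30% v 40% gives 49% v 58%, −9.
- Break-even: at 40%/15% and independence, counting all events reverses an excess smaller than 26.5 points (placebo other rate 10%), falling to 14.7 points (placebo other rate 50%).
- Equal COVID-19 rates of 40%: 58% v 52%, so +10 becomes +6 with no reversal.

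**A second use of the same count.** The interim toxicity criteria in Section 13 include "If the percentage of grade 3/4 all-cause adverse events is at least 15% higher in the ibrutinib arm". With 15 patients per arm, the 20% v 30% assumption, 15% read as percentage points and every event taken as grade 3/4, the chance of meeting this criterion is 33.5% with progression excluded and 6.0% with it counted. Fatal events would not be grade 3/4, so this gap is probably overstated.

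**The case against.** The strongest reply is that the planned output already separates these events. Section 13 summarises by type and by attribution, so respiratory failure that was recorded would have its own row, and an excess of bleeding, cardiac events or infection would show in theirs. Section 9.6 classes an event as not related when the underlying condition explains it sufficiently, so COVID-19 respiratory failure would normally leave the treatment-related summary. The analysis is descriptive. Treating physicians and assessors are blinded (7.1.2), and the trial has one centre (6.2) and weekly toxicity calls (9.9).

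Most of this stands. A reader might infer that a real toxicity excess would vanish from the report; the breakdown by type and attribution does not support that. What remains exposed is the pooled all-cause grade 3+ count. Blinding prevents coding that depends on arm, but a rule applied equally still adds more events to the arm with more progression. An event never recorded as an AE also cannot appear in a breakdown of AEs by type.

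A reader might also infer that the wording by itself reverses the safety comparison. It does not. Reversal needs ibrutinib to reduce COVID-19 events, a moderate excess of other toxicity for which the documents give no rates, and a fatal share that is not too large.

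Finally, the 9.3 wording can be read as a general exclusion with a specific override for death. That is fair, but it leaves non-fatal respiratory failure unsettled.

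**Conclusion.** The contradiction in 9.2 is real. It is limited to progression that is both significant and expected, but that class includes the trial's main event. The all-cause grade 3+ comparison by arm therefore has no single definition, and counting progression moves it toward the efficacy result.

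In the illustration the two readings lie 21.5 × (1 − s) points apart: from up to 10 points against ibrutinib to 11.5 points in its favour. This rests on the full design effect, the assumed 20% and 30% rates, independence, and the same fatal share in both arms. With no effect on COVID-19 events, counting them only dilutes the difference. The treatment-related summary is affected only if progression is attributed to study drug. No hypothesis test, error rate or power figure changes. The wording should be corrected, and the change is small.

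**What to change.** - In 9.2 and 9.3, state one rule for recording COVID-19 progression, so that the two lines of 9.2 agree with each other and with the SAE section. Deaths continue to be reported as SAEs.
- Record progression events in every patient with a flag, so that neither version of the count depends on an investigator's reading.
- In Section 13, tabulate grade 3+ AEs by arm both with and without events attributed to COVID-19 progression. Both versions keep any respiratory failure or death judged possibly related to study drug or due to another cause. Removing every primary-endpoint event would be wrong: that endpoint does not restrict the cause of respiratory failure, and Section 4.5 names bleeding and secondary infection as concerns with ibrutinib.
- State which version the Section 3.2 toxicity endpoint uses, and which count the interim toxicity criteria read.

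The cost is wording in 9.2, 9.3, 3.2 and 13, one data flag and one extra table.

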9.3. Definition of a Serious Adverse Event (SAE)

An AE that meets one or more of the following criteria/outcomes is classified as serious:

- Death.
- Life threatening.
- Disabling/incapacitating.
- Results in new hospitalization or prolongs a hospital stay.
- A congenital abnormality.
- Other serious medical events may also be considered SAEs if it is an important medical event that may not be immediately life threatening or result in death or hospitalization, but based upon appropriate medical and scientific judgment may jeopardize the patient or may require medical or surgical intervention to prevent one of the other serious outcomes listed in the definition above.

Death for any reason must be reported as a SAE.

A SAE does not include:

- Progression of the underlying infection or syndrome (COVID-19).
- Hospitalization for a routine clinical procedure or treatment as required by the protocol.

- Hospitalization for non-medical reasons (i.e., social admissions, hospitalizations for social, convenience, or respite care).

